7.3.5. Subject withdrawal

Subjects can withdraw informed consent at any time for any reason during the clinical investigation. The investigator can decide to withdraw a subject from the study for urgent medical reasons. Normal clinical standard of care will be followed to obtain a diagnosis.

7.4. Procedures

The flowchart for current clinical practice and study practice CBCT-guided navigation bronchoscopy are depicted in *Figure 3* below.

Current clinical practice

- Pre-procedural*

In current clinical practice, the lesion identification and trajectory planning are performed by interventional pulmonologists who need to mentally reconstruct the navigation trajectory (mind-map) based on the available CT-images in routine DICOM viewers.

- Intra-procedural*

The procedure starts with an inspection bronchoscopy to examine the trachea and proximal airways. If the tumour is not visible endobronchially, navigation bronchoscopy is continued by advancing a pre-formed curvature catheter through the bronchoscope under image guidance. Advanced imaging with CBCT and AF will expedite catheter guidance through the airways. The CBCT gives feedback about the position of the catheter in a three-dimensional space. Once tool-in-lesion is confirmed with either rEBUS, rapid on-site evaluation (ROSE) and/or CBCT, tissue sampling is performed. If indicated, an EBUS is performed for staging lung cancer.

Study practice

- Pre-procedural*

In this study, pre-procedural planning will be performed with Philips' AirWaze software. The CT-scan is loaded into the software system and the airways will be segmented and visualized. The target lesion is segmented with a one-click segmentation by the physician and is followed by a selection of the pathway to the target lesion.

IGT Systems	Feasibility Clinical Investigation Protocol AirWaze – easy and advanced tools for CBCT guided lung interventions	Doc ID: XCY607-130895 Rev: 04 Date: 2024-Jun-19 Page 23 of 56
-------------	--	--

- *Intra-procedural*

As performed routinely, an inspection bronchoscopy is performed at the start of the procedure. The selected pathway to the target lesion from the planning will be registered to and overlayed on the first performed CBCT. This overlay is visible at any time and will help the physician guide to the target lesion. If CBCT is indicated in conventional procedures, a low-dose CBCT-FluoroSweep scan will be performed of the same catheter and tool position. The CBCT-FluoroSweep has the same function as the regular CBCT, but it will be evaluated whether the low-dose CBCT-FluoroSweep is as accurate as the CBCT. Once tool-in-lesion is confirmed with either rEBUS, ROSE and/or CBCT-FluoroSweep (with regular CBCT as gold standard), tissue sampling is performed. If indicated, an EBUS is performed for staging lung cancer.

Follow-up

Safety follow-up visit will take place 1 week post-procedure (+7 days / -2 days). This visit may occur via phone or clinic visit. All adverse events that have occurred until this visit will be collected and monitored, including any prolonged hospital stay because of procedural complications, as well as unexpected complications.

[figure not shown]

Figure 3. Flowchart of the CBCT-guided navigation bronchoscopy procedure of the current clinical practice (bottom flow) and study practice with the AirWaze investigational device (top flow).

*Will be excluded from the PP population, see section 8.1.

7.5. Monitoring Plan

Monitoring will be performed by a trained person appointed by Philips to ensure compliance with the feasibility clinical investigation protocol, applicable national regulations and international standards, patient safety and data validity. The Sponsor may designate one or more individuals to monitor the progress of a clinical study. The Sponsor may also delegate the monitoring responsibilities to a third party. However, the Sponsor remains ultimately responsible for the conduct of the study. The Institution is responsible for the appropriate de-identification of subject data. The investigational site should provide access to the source data of the subjects.

The first visit will occur as soon as possible after the first subject is enrolled at each study site. The monitoring schedule is based on the following considerations: enrollment rate, study compliance at the center, the magnitude of data corrections required, the complexity of the feasibility clinical investigation, IRB/MEC request, and audit/inspection.

The monitor activities include:

IGT Systems	Feasibility Clinical Investigation Protocol AirWaze – easy and advanced tools for CBCT guided lung interventions	Doc ID: XCY607-130895 Rev: 04 Date: 2024-Jun-19 Page 24 of 56
-------------	--	--

- Check that the study is conducted, recorded and reported in compliance with the clinical protocol, good clinical practice, and applicable regulations. Acts to oversee the progress of the study.
- Check signed and dated informed consent of the subjects and check that this is signed before any study-related procedures are undertaken.
- Ensure that essential documents (e.g., legal contract, MEC/IRB approval) are maintained in the Site Regulatory File.
- Ensure recording of deviations from protocol and store in Site Regulatory File or e-CRF.
- Ensure that all adverse events and device deficiencies are reported to the sponsor, and all serious adverse events and device deficiencies that could have led to a serious adverse device effect are reported to the sponsor without unjustified delay.
- Ensure that applicable adverse event and device deficiency are reported to the MEC/IRB and Competent Authority (if applicable) within the required timeframe.
- Ensure that the principal investigator is informed and knowledgeable of all relevant document updates concerning the feasibility clinical investigation (e.g., feasibility clinical investigation protocol and Investigator Brochure). Ensure that substantial amendments to the protocol and/or Investigators Brochure are submitted to the MEC/IRB and/or Competent Authority (if applicable) if required by the national regulations.
- Ensure device accountability.

Critical data and processes will be monitored for this study prior to clinical report completion based on a selective monitoring approach. The monitor activity solely involves the review of critical clinical data that effect study endpoints. Data collection for reasons other than to support the protocol-defined endpoints will not be monitored. A site close-out visit will be conducted once the site has completed collecting data for the study.

Details of the monitoring approach and names of the involved monitor(s) will be laid down in the Monitoring Plan.

8. Statistical considerations

8.1. Analysis Populations

The following analysis populations will be defined in this study:

Enrolled Population

The enrolled population is defined as all subjects who signed informed consent during the study.

Intention-to-treat Population

The intention-to-treat population (ITT) is defined as all subjects in the Enrolled Population that have undergone the CBCT-guided navigation bronchoscopy procedure as depicted in *Figure 3* because suspected pulmonary lesions with intermediate to high risk of malignancy in early-stage disease were found on pre-procedural CT scans.

Per Protocol population

The Per Protocol population (PP) is defined as all ITT subjects without major protocol deviations. Protocol deviations will be divided into major protocol and minor protocol deviations. A major protocol deviation is one that may impact subject safety, affect the integrity of study data and/or affect subject's willingness to remain in the study. An example of a major violation is enrolling a participant who did not meet all the inclusion/exclusion criteria or failing to obtain or document informed consent prior to initiation of study procedures. Major protocol deviations would exclude the subject from the PP population.

Minor protocol deviations are those that are not considered to significantly affect the primary endpoint analysis and hence do not warrant subjects' exclusion from the PP population.

Subjects with a tumor location endobronchial found during the inspection bronchoscopy and therefore not require the CBCT-guided navigation bronchoscopy (as displayed in *Figure 3*), will be excluded from the PP population.

The PP population will be the primary population for the analyses as described in study objectives and endpoints.

IGT Systems	Feasibility Clinical Investigation Protocol AirWaze – easy and advanced tools for CBCT guided lung interventions	Doc ID: XCY607-130895 Rev: 04 Date: 2024-Jun-19 Page 25 of 56
-------------	--	--

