7.3.3. Number of subjects

A total of 37 prospectively included subjects in the Intention-To-Treat population are necessary to collect sufficient data for the evaluation of the primary and secondary objectives of this clinical investigation. After applying a drop-out rate of 10% of subjects will be lost, a total of 33 subjects in the Per Protocol population is required. More information on the statistical considerations can be found in Section 8.

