8.2. Sample Size Justification

A total of 37 patients will be included in this feasibility study. The physicians are familiar with the AirWaze investigational device in a non-clinical setting. The clinical setting will function as clinical and technical de-risking of the software program and the information from this study will be used to design a robust pivotal claim-driven study. Semi-structured questionnaires will be used to assess the overall system usability and the accuracy of the AirWaze CBCT-FS scan. Furthermore, the number of imaging and algorithm failures and the ability to work around quickly will be evaluated. Taking into account a 10% drop-out rate, it is expected by experts that a Per Protocol population of 33 patients is sufficient to de-risk the AirWaze features.

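### Performance endpoints are read in a Per Protocol set with a loosely worded exclusion rule and no ITT analysis beside it, so one exclusion can decide the 90% or <5% mark

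*Combined protocol and SAP*

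**What the plan says.** Section 8.1 defines an enrolled, an ITT and a PP population and then states: "The PP population will be the primary population for the analyses as described in study objectives and endpoints". PP is ITT minus subjects with major deviations. The rule begins "A major protocol deviation is one that may impact subject safety, affect the integrity of study data" and extends to the subject's willingness to continue. Its two examples are enrolling someone ineligible and failing to obtain or document consent in time. A deviation counts as minor, and the subject stays in, if it is thought not to have a significant effect on the primary endpoint analysis. Subjects whose tumour proves to be endobronchial at inspection are also removed from PP.

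The ITT definition requires that navigation bronchoscopy was done, and adds a reason clause about lesions with "intermediate to high risk of malignancy in early-stage disease". That condition is not an inclusion criterion in 7.3.1.1 and is not among the baseline items in 8.5.

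On numbers, section 7.3.3 says "A total of 37 prospectively included subjects in the Intention-To-Treat population are necessary to collect sufficient data" and that "a total of 33 subjects in the Per Protocol population is required". Section 8.2 rests the 33 on expert judgement.

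Other populations do appear. Sections 8.7.7 to 8.7.9 analyse adverse events, adverse device effects and device deficiencies in all subjects. Section 8.3 lists all data for the enrolled population, and section 8.4 lists why a subject was not evaluated.

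**The concern.** Section 8.2 gives the purpose as clinical and technical de-risking, including a count of imaging and algorithm failures, to inform a pivotal study. An analysis set for that purpose should not be able to lose failures by a judgement made once results are known.

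Three features leave that possibility open.

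- **The wording is broad.** A deviation need only be one that may affect data integrity. Sections 7.4 and 8.1 leave unclear whether a procedure completed without the software, or with an unusable CBCT-FS, is such a deviation. Table 4 foresees a permanent malfunction after which the user carries on without the tool.
- **The major/minor split turns on perceived effect on the primary endpoint analysis.** That ties inclusion to the result.
- **No safeguard is stated.** Section 8 does not say who grades deviations, when, or without sight of what. Section 11 has the sponsor review deviations. Section 9 locks the database at the start of the final analysis and mentions no grading step before that. The operator's Appendix II answers may already be recorded by then.

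At stake are the two numerical read-outs most likely to be carried forward: the 90% accuracy mark (8.6) and the <5% algorithm-failure mark (8.7.2).

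**Working it through.** **Inputs.** ITT target 37 and PP requirement 33 (7.3.3); drop-out 10% (8.2); accuracy mark 90%, a point estimate over CBCT-FS/CBCT pairs (8.6); algorithm-failure mark <5% of cases (8.7.2); 1-3 CBCT-FS scans per procedure (Appendix VI, Table 7).

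**The plan's own figure.** 33 / (1 - 0.10) = 36.67, rounded up to 37. This reproduces. The planned loss is 37 - 33 = 4 subjects. The 33 has no alpha, power or precision behind it, so it cannot be derived.

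**Where the marks fall, taking one result per subject (assumption).**

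| Set | Needed for accuracy of at least 90% | Discordant results allowed | Algorithm failures allowed for <5% |
|---|---|---|---|
| 37 | 34 (91.9%) | 3 | 1 (2.7%) |
| 36 | 33 (91.7%) | 3 | 1 (2.8%) |
| 33 | 30 (90.9%) | 3 | 1 (3.0%) |

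The number of adverse results allowed is the same at 33, 36 and 37. Removing an adverse subject therefore uses up none of the margin.

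**One adverse subject removed.**
- Accuracy: 33/37 = 89.2% (misses) becomes 33/36 = 91.7% (meets).
- Algorithm failures: 2/37 = 5.4% (misses) becomes 1/36 = 2.8% (meets).

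**Worst case: all four planned losses are adverse.**
- Accuracy: 30/37 = 81.1% becomes 30/33 = 90.9%.
- Algorithm failures: 5/37 = 13.5% becomes 1/33 = 3.0%.

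**More than one pair per subject.** With 2 pairs each, PP has 66 pairs and needs 60; the lowest accuracy in all 37 subjects that still passes in PP is 60/74 = 81.1%. With 3 pairs each it is 90/111 = 81.1%. The worst-case floor does not depend on the number of pairs.

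**How often the verdict would change.** The number of discordant results among 37 is taken as binomial at an assumed true accuracy, and four subjects are then removed. The documents give no true accuracy, so a range is shown.

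| Assumed true accuracy | Four removed at random: accuracy verdict differs | Up to four discordant subjects removed: ITT miss becomes PP pass |
|---|---|---|
| 85% | 7.6% | 64.5% |
| 90% | 9.0% | 48.6% |
| 95% | 3.1% | 11.1% |

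The first column is the expected effect if exclusions have nothing to do with outcome. The second is an upper bound for selective exclusion.

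**The case against.** The case against is substantial.

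- **Failures have other routes into the report.** Device deficiencies, which by definition include malfunctions, are reported for all subjects, and listings cover the enrolled population. A careful reader could recount. This stands, and it means the PP rule does not govern every endpoint. But a recount from listings is not a pre-specified read-out against the 90% and <5% marks.
- **A software failure is not in itself a departure from the protocol.** Both examples of major deviations concern eligibility or consent. The questionnaires collect failures as outcomes, with an inconclusive option for CBCT-FS and failed columns for each algorithm. A reader might infer that the plan intends to drop failed procedures; nothing in the documents says so. What remains is that nothing rules it out.
- **SUS.** A reader might think usability is biased too. It is scored per operator every four procedures, so a subject-level exclusion has no defined effect on it.
- **ITT does not cure everything.** Accuracy is computed over pairs. If no CBCT-FS was acquired there is no pair, and an ITT analysis does not restore it.
- **Four is a planning allowance.** It is neither a cap nor a licence to exclude, and its resemblance to the 10% error margin means nothing. The number required is the PP 33, of which 37 is the inflation. Naming PP as primary does not bar an ITT analysis.
- **The malignancy-risk clause may be only background** on why patients have the procedure. That is plausible, but it sits inside a population definition and PP is a subset of ITT. Read literally, it leaves an eligible treated subject without a place in either set.
- **The study is single-arm, descriptive and already enrolling.** The opening of 8.7 even says the secondary objectives carry no performance requirements, although 8.7.2 sets the <5% mark. This limits the severity, and full blinding of deviation grading may be hard to achieve at this stage.

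**Conclusion.** The point holds for the performance endpoints: CBCT-FS accuracy, algorithm quality and failures, and plan quality. They are read in PP, no ITT analysis of them is specified, and the exclusion rule is broad, with no closed list, timing or blinding. A single exclusion can decide a result just below either mark.

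The size depends on whether exclusions relate to outcome. If they do not, the accuracy verdict changes in about 3-9% of trials at assumed true accuracies of 85-95% with four subjects lost. The drop from 90.9% in PP to 81.1% in ITT needs every loss to be an adverse result, which the documents do not predict. The counts assume one result per subject, except for the 81.1% floor, which also holds at two or three pairs each.

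The documents do not support the stronger conclusions that every endpoint depends on PP, that failures will be removed, or that ITT must be the sole headline. This is a cheap improvement to a feasibility plan and does not invalidate it.

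**What to change.** In 8.1, 8.6 and 8.7.2:

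1. Report accuracy and algorithm failures in ITT, defined as all subjects in whom CBCT-guided navigation bronchoscopy with AirWaze was started, beside PP. Give the reason for each exclusion and state whether the 90% and <5% marks are met in both sets.
2. State that device, software or imaging failure is not a major deviation.
3. Classify deviations before database lock, without reference to the Appendix II agreement results.
4. Delete the clause on malignancy risk and early stage from the ITT definition, or align it with the inclusion criteria.
5. Report procedures with no CBCT-FS as a separate count, since they contribute no pair in either set.

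The cost is wording in the plan and one extra table column. The ITT figure may be slightly less favourable than the PP figure.

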- Quality of the automatic device detection is considered sufficient when the average Likert score equals or is higher than 4. For this categorical variable, counts and percentages will be calculated as well.
- Algorithm failures are acceptable when in <5 % of the cases for pulmonary lesions algorithm failures related to CBCT or CBCT-FS occurred.

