Significant changes (such as device modifications, and study procedures) shall be agreed upon with the principal investigator. Significant changes shall be submitted to and approved by the MEC and the Competent Authority (if applicable) before implementation. Exempt from this requirement are measures which have to be taken immediately in order to protect the participants.

If the amendment impacts the integrity of the clinical investigation, the data collected before and after the amendment shall be analyzed statistically to assess the effect of the amendment on endpoint analysis. This analysis shall be included in the clinical investigation report.

11. Deviations from the feasibility clinical investigation protocol

The investigator is not allowed to deviate from the feasibility clinical investigation protocol (CIP) neither to enroll subjects that do not comply with all inclusion and exclusion criteria. Under emergency circumstances, deviations from the CIP to protect the rights, safety and well-being of human subjects may proceed without prior approval of the sponsor and the MEC. Such deviations shall be documented and reported to the sponsor and the MEC as soon as possible. The principal investigator shall promptly report any deviations from the CIP that affect the rights, safety or well-being of the subject or the scientific integrity of the clinical investigation, including those which occur under emergency circumstances, if required by the MEC or national regulations.

IGT Systems	Feasibility Clinical Investigation Protocol AirWaze – easy and advanced tools for CBCT guided lung interventions	Doc ID: XCY607-130895 Rev: 04 Date: 2024-Jun-19 Page 32 of 56
-------------	--	--

All deviations from the CIP will be documented with date, subject, reason, actions taken and if the deviation affects the subject's rights, safety and well-being or the scientific integrity of the feasibility clinical investigation. The deviation shall be notified to the sponsor as soon as possible via the site monitor. Deviations shall be discussed with the principal investigator(s) or authorized designer. Deviations will be reviewed by the sponsor and in case of serious or repetitive deviations, a corrective action plan may represent a need to initiate a corrective action plan with the principal investigator. In some cases, termination or suspension of the participation of a particular site or investigator.

12. Device accountability

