15.3. Anticipated adverse device effects

Anticipated adverse device effects are described below in *Table 4*.

Table 4. Anticipated adverse device effects.

Anticipated adverse device effects		Severity	Likely incidence (PoH)	Risk category	Mitigation or treatment
Hazardous situation	Possible harm				
Wrong treatment decisions due to errors or missing information in Investigational Device.	Patient exposed to inadequate / inappropriate treatment or diagnostic exposure during clinical use (F10)	S1	PoH 2 - Not expected to occur (10— <100 per 1000000)	Acceptable	Add a message in the user manual stating that feature is not for clinical decision-making.
Permanent malfunction of the Interventional Tool or Interventional Workstation during an interventional procedure due to software or hardware failure. The result is that the user needs to continue the procedure on X-Ray modality without the Interventional Tool.	No Health Consequences or Impact (F26)	S0	PoH 2 - Not expected to occur (10— <100 per 1000000)	Acceptable	No measures need to be taken
The C-arc has been moved in the longitudinal and/or transversal direction invalidating the current registration.	Patient exposed to incorrectly deployed biopsy/ablation tools during clinical use Possible harm is: - Bronchial hemorrhage (E0707) - Pneumothorax (E0734) - Procedure related complications (E21) - Delay to treatment/therapy (F05)	S2	PoH 2 - Not expected to occur (10— <100 per 1000000)	Acceptable	In the IFU, inform the clinical user that the C-arc should not be moved in the longitudinal and/or transversal direction anymore after planning, and what the possible impact is when it happens.
The planned path is not at the right location due to a badly geometrically calibrated system (deviation after a long use), so the geometry space of 3D image is not matching the geometry space of 2D images (fluoro).	Patient exposed to incorrectly deployed biopsy/ablation tools during clinical use Possible harm is: - Bronchial hemorrhage (E0707) - Pneumothorax (E0734) - Procedure related complications (E21) - Delay to treatment/therapy (F05)	S2	PoH 2 - Not expected to occur (10— <100 per 1000000)	Acceptable	Standard (field) service procedures will detect and correct badly calibrated systems.

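### The performance verdicts rest only on a per-protocol set defined by open-ended deviation classes, with no intention-to-treat result beside it

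*Combined protocol and SAP*

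**What the plan says.** Section 8.1 defines three sets: Enrolled, ITT and PP. The link between the last two is that "The Per Protocol population (PP) is defined as all ITT subjects without major protocol deviations". PP is then made primary: "The PP population will be the primary population for the analyses as described in study objectives and endpoints".

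The two deviation classes use different tests. On one side, "A major protocol deviation is one that may impact subject safety, affect the integrity of study data", or affect the subject's willingness to stay. On the other, "Minor protocol deviations are those that are not considered to significantly affect the primary endpoint analysis". The only examples of a major deviation are an eligibility breach and missing consent, and there is no closed list. Subjects whose tumour proves to be endobronchial also leave PP.

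On who decides, section 11 says "Deviations will be reviewed by the sponsor". It asks that each deviation be recorded with whether it affects scientific integrity. No section says when a deviation is classed as major or minor, or that this is done without sight of the readings. Section 9 says only that the database is locked at the start of the final analysis.

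ITT appears in the planned numbers (section 7.3.3: "A total of 37 prospectively included subjects in the Intention-To-Treat population are necessary to collect sufficient data") and as the base for PP. Sections 8.6 to 8.7.6 do not use it. Two of the criteria judged in those sections are accuracy of 90% over CBCT-FS/CBCT pairs (8.6) and, in 8.7.2, "Algorithm failures are acceptable when in <5 % of the cases for pulmonary lesions". Adverse events, adverse device effects and device deficiencies (8.7.7 to 8.7.9) use all subjects, and data listings cover the enrolled population (8.3).

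**The concern.** The study is single-arm and unblinded, it has pass marks, and the operators' answers are known as the procedures happen. In that setting a set defined by judgement should either be fixed in advance or be shown beside one that is not. The plan does neither for its performance endpoints.

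The two deviation tests are not complements. A deviation can touch safety and leave the primary endpoint analysis unaffected, so it meets both descriptions, and someone must choose. Data integrity is also a broad ground.

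The procedures of interest are those in which the study steps were not completed because something in the device or imaging went wrong. Table 4 in section 15.3 foresees one such case: "The result is that the user needs to continue the procedure on X-Ray modality without the Interventional Tool". The steps in section 7.4 (overlay, and a CBCT-FS at the same position as each indicated CBCT) would then be missed in part. Nothing says that such a procedure must stay in PP. Section 8.2 gives de-risking and the evaluation of imaging and algorithm failures as the purpose of the study, so these procedures are part of what it is meant to measure.

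**Working it through.** **Inputs.** ITT 37 and PP 33 (7.3.3); drop-out 10% (8.2); accuracy mark 90%, counted over pairs (8.6); algorithm-failure limit <5% of cases (8.7.2); 1 to 3 CBCT-FS acquisitions per procedure (Appendix VI, Table 7).

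**The plan's own figure.** 33 / (1 − 0.10) = 36.67, rounded up to 37. This reproduces. The 33 is an expert expectation and cannot be derived. The gap is 37 − 33 = 4 subjects.

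**Assumptions for the illustration.** Four ITT subjects are outside PP. Every procedure supplies the same number of pairs, k = 1, 2 or 3. The number of excluded pairs that are discordant is varied, because the documents give no rate.

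**Accuracy.** The lowest PP pass is the smallest whole number that is at least 0.9 × 33k. The ITT value is (that number + 4k − x) / 37k, where x is the number of discordant pairs among the 4k excluded.

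| k | Lowest PP pass | ITT, x = 0 | Last x at which ITT passes | First x at which ITT misses |
|---|---|---|---|---|
| 1 | 30/33 = 90.9% | 34/37 = 91.9% | x = 0 | x = 1: 33/37 = 89.2% |
| 2 | 60/66 = 90.9% | 68/74 = 91.9% | x = 1: 67/74 = 90.5% | x = 2: 66/74 = 89.2% |
| 3 | 90/99 = 90.9% | 102/111 = 91.9% | x = 2: 100/111 = 90.1% | x = 3: 99/111 = 89.2% |

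At the margin the two sets therefore disagree after 1, 2 or 3 discordant pairs, which is one procedure's worth in each row.

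**Algorithm failures, taking a case as a procedure.** The most that PP allows is 1/33 = 3.0%, since 2/33 = 6.1%. One excluded failure makes 2/37 = 5.4% in ITT, above the limit.

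**SUS.** Section 8.6 collects one form per operator every four procedures, and Appendix I expects about nine (37 / 4 = 9.25). A single subject cannot be removed from a form that covers four procedures, so the PP rule cannot be applied to this primary endpoint.

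**The case against.** The strongest reply is that nothing in the documents makes a device failure a protocol deviation. The examples of a major deviation concern eligibility and consent. Failure is collected as an outcome: 8.7.2 makes it an endpoint, and Appendix IV has a failed box for segmentation, registration and detection. This stands. A reader might infer that AirWaze failures are removed from PP by rule, and the text does not support that. What remains is that a departure from study steps caused by a failure is not protected from being graded major.

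Table 4 rates the loss of the tool at 10 to <100 per 1,000,000. Over 37 procedures that is fewer than 37 × 100 / 1,000,000 = 0.0037 expected events. If the tool is lost before a paired scan, there is no pair, and accuracy is unchanged in either set. Both points stand. The Table 4 case shows that the route is foreseen, not that it is frequent. For accuracy, the exposure is limited to procedures that yielded at least one pair.

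It is tempting to set 30/37 = 81.1% in ITT against 30/33 = 90.9% in PP. That needs all four exclusions to be discordant at one pair each. It is the extreme case, and some of the four may be endobronchial tumours or other losses unrelated to the device.

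A reader might also infer that failures would vanish from the report, or that dose would be biased favourably. Neither follows. The enrolled-population listings, the listed reasons for non-evaluation (8.4) and the all-subject deficiency tables would still show the failures. A procedure continued without AirWaze omits CBCT-FS dose but may use more fluoroscopy, so the direction for dose is open.

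Finally, the wording on minor deviations concerns whether the analysis is affected, not which way the result moves. That is correct. It is a loose criterion, not a rule that selects on success.

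**Conclusion.** The point holds as a gap in the plan. The only population assigned to the performance endpoints can be reduced by judgement after the procedure, under overlapping definitions, with no stated timing or blinding and no ITT result for comparison. In a set of 33, one procedure is enough to separate the two populations at the pass mark, for accuracy and for algorithm failures alike. This rests on four exclusions, equal pairs per procedure and a result close to the mark. Away from the mark, one procedure would change the figure but not the verdict. How many exclusions would be device-related is not known from the documents, and no bias in a particular direction is shown.

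The study is a descriptive feasibility study with no test on SUS, and section 8.7 says that the secondary objectives carry no performance requirements, although 8.7.2 sets the <5% limit. The change should be made, but the design does not fail without it.

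**What to change.** In section 8.1:

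1. Report the accuracy and algorithm-failure verdicts, and the other per-procedure performance endpoints, in all validly consented ITT subjects in whom AirWaze was used or attempted, beside the PP result. Including attempted use keeps in procedures where the software failed before navigation. Requiring valid consent keeps out subjects whose data should not be analysed.
2. State that device, software or imaging failure, and continuing without AirWaze, are never in themselves grounds for exclusion from PP.
3. Replace the test based on the effect on the primary endpoint analysis with a closed list of major deviations. Fix the list, and apply it from the deviation log, before database lock and without access to the endpoint data.
4. State that SUS is summarised over all completed forms, because each form spans four procedures.

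The cost is a wording change and one extra column per table. Some headline figures may be less favourable. No further data collection or subjects are needed.
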